219239  
Protocol

AUC(0-inf)	Area under the concentration-time curve from time zero extrapolated to infinity
AxMP	Auxiliary medicinal product
C3/C4	Complement component 3/ Complement component 4
CA	Competent authority
CHB	Chronic hepatitis B
Cmax	Maximum observed plasma concentration
COVID-19	Coronavirus disease 2019
CRF/eCRF	Case report form/electronic case report form
CSR	Clinical study report
CV	Coefficient of variation
CVb	Between subject coefficient of variation
DAIDS	Division of AIDS

**CONFIDENTIAL**219239  
Protocol

Abbreviation	Definition
DIVI	Drug Induced Vascular Inflammation
ECG	Electrocardiogram
eGFR	Estimated glomerular filtration rate
FDA	Food and Drug Administration, United States of America
GCP	Good clinical practices
GFR	Glomerular filtration rate
GSK	GlaxoSmithKline
HBcAb	Hepatitis B core antibody
HBsAg	Hepatitis B surface antigen
HCP	Healthcare professionals
HIV	Human immunodeficiency virus
hs-CRP	High-sensitivity C-reactive protein
IB	Investigator's brochure
ICF	Informed consent form
ICH	International Council on Harmonisation
ICSR	Individual case safety reports
IEC	Independent ethics committee
IFU	Instructions for use
IMP	Investigational medicinal product
INR	International normalized ratio
IRB	Institutional review board
MDR	Medical Device Regulation
MedDRA	Medical Dictionary for Regulatory Activities
NIMP	Non-investigational medicinal product

**CONFIDENTIAL**219239  
Protocol

Abbreviation	Definition
NQ	Non-quantifiable
PCR	Polymerase chain reaction
PFS	Prefilled syringe
PK	Pharmacokinetic
PT	Prothrombin time
QTL	Quality tolerance limit
RPGN	Rapidly progressive glomerulonephritis
SADE	Serious adverse device effect
SAE	Serious adverse event
SAP	Statistical analysis plan
SARS	Severe acute respiratory syndrome coronavirus
SoA	Schedule of activities
SOC	System organ class
SPEP	Serum Protein Electrophoresis
SRT	Safety Review Team
SSD	Safety syringe device
TEAE	Treatment-emergent adverse event
THC	Tetrahydrocannabinol
UPEP	Urine Protein Electrophoresis
USADE	Unanticipated serious adverse device effect
WBC	White blood cell
WOCBP	Woman of childbearing potential
WONCBP	Woman of nonchildbearing potential

**CONFIDENTIAL**

219239

Protocol

Term	Definition
Certified copy	A copy (irrespective of the type of media used) of the original record that has been verified (i.e. by a dated signature or by generation through a validated process) to have the same information, including data that describe the context, content, and structure, as the original.
Eligible	Qualified for enrollment into the study based upon strict adherence to inclusion/exclusion criteria.
Essential documents	Documents which individually and collectively permit evaluation of the conduct of a study and the quality of the data produced
Intervention number	A number identifying an intervention to a participant, according to intervention allocation.
Investigational medicinal product	An IMP is a pharmaceutical form of an active substance or placebo being tested or used as a reference in a clinical study, including products already with a marketing authorization but used or assembled (formulated or packaged) in a way different from the authorized form, or when used for an unauthorized indication, or when used to gain further information about the authorized form. Medicinal products with a marketing authorization are IMPs when they are to be used as the test substance, reference substance, or comparator in a clinical study, provided the requirement(s) in the definition is/are met.
Investigator	
A person responsible for the conduct of the clinical study at a study site. If a study is conducted by a team of individuals at a study site, the investigator is the responsible leader of the team and may be called the principal investigator.
 
The investigator can delegate study-related duties and functions conducted at the study site to qualified individual or party to perform those study-related duties and functions

NIMP/AxMP AxMP	A NIMP or AxMP is a medicinal product that is not classified as an IMP in a study, but may be taken by participants during the study, e.g., concomitant or rescue/escape medication used for preventive, diagnostic, or therapeutic reasons or medication given to

**CONFIDENTIAL**219239  
Protocol

Term	Definition
	ensure that adequate medical care is provided for the participant during a study.
Participant number	A unique identification number assigned to each participant who consents to participate in the study.
Participant	
Term used throughout the protocol to denote an individual who has been contacted to participate or who participates in the clinical study as a recipient of the study intervention (vaccine(s)/product(s)/control).
 
Synonym: subject

Primary Completion Date	
The date on which the last participant in a clinical study was examined or received an intervention to collect final data for the primary outcome measure.
 
Whether the clinical study ended according to the protocol or was terminated does not affect this date. For clinical studies with more than one primary outcome measure with different completion dates, this term refers to the date on which data collection is completed for all the primary outcome measures.

Randomization	Process of random attribution of intervention to participants to reduce selection bias.
Source data	All information in original records and certified copies of original records of clinical findings, observations, or other activities in a clinical study necessary for the reconstruction and evaluation of the study. Source data are contained in source documents (original records or certified copies).
Study intervention	
Term used throughout the clinical study to denote a set of investigational product(s) or marketed product(s) or placebo intended to be administered to a participant.
 
Note: “Study intervention” and “study treatment” are used interchangeably unless otherwise specified.

Study completion date	The date on which the last participant in a clinical study was examined or received an intervention/treatment to collect final data for the primary outcome measures, secondary outcome measures, and AEs (that is, the last participant's last visit or LSLV).

**CONFIDENTIAL**219239  
Protocol

## 1. PROTOCOL SUMMARY

### 1.1. Synopsis

**Protocol Title:** A Phase 1, randomized, open-label, parallel group study to evaluate the relative bioavailability of subcutaneous bepirovirsen when delivered from a vial or prefilled syringe fitted with a safety syringe device in healthy adult participants

**Brief Title:** A study to evaluate the relative bioavailability of subcutaneous bepirovirsen when delivered from a vial or prefilled syringe fitted with a safety syringe device in healthy adult participants

**Rationale:** Refer to Section 2.1.

**Objectives, Endpoints, and Estimands:** Refer to Section 3.

**Overall Design:** Refer to Section 4.1.

**Number of Participants:** Refer to Section 9.5.

[figure not shown]
**Data Monitoring/Other Committee:** Refer to Section 10.1.5.

CONFIDENTIAL

219239  
Protocol

## 1.2. Schema

[figure not shown]
Figure 1 Study Design Overview

CONFIDENTIAL

219239  
Protocol

Figure 2 Study Design

Randomized 3:3:2:2 to Groups 1-4. Randomization schedule also includes injection site: upper arm, abdomen, or thigh (1:1:1) in Groups 1 and 2, and abdomen or thigh (1:1) in Groups 3 and 4. Recruitment into all groups to proceed in parallel.

CONFIDENTIAL

219239  
Protocol

### 1.3. Schedule of activities (SoA)

**Table 1** Screening Visit

Procedure	Screening (up to 28 days before first dose)	Notes
Informed consent	X	
Inclusion and exclusion criteria	X	
Demography	X	
Past and current medical conditions	X	
Full physical examination including height and weight	X	At a minimum, assessments of the skin, cardiovascular, respiratory, gastrointestinal, and neurological systems.
Vital signs	X	Blood pressure and heart rate in triplicate; mean of 3 measurements used to confirm eligibility. Respiratory rate and temperature, single measurements.
COVID-19 test	X	Using a PCR or antigen test approved by the country regulatory authorities.
Human immunodeficiency virus, hepatitis B and C screening	X	If test otherwise performed within 3 months before first challenge day, testing at screening is not required.
Medication/drug/alcohol history	X	Includes substance usage and current medical condition.
Drug, alcohol, and cotinine screen	X	As per standard local practice.
12-lead ECG	X	In triplicate; mean of 3 measurements used to confirm QTc eligibility.
Follicle-stimulating hormone	X	As needed, to confirm postmenopausal status.
Serum pregnancy test	X	WOCBP only.
Clinical chemistry, hematology and urinalysis	X	
Urine ACR	X	
C3, C4, hs-CRP, p-ANCA, c-ANCA	X	MPO-ANCA and PR3-ANCA to be performed if p-ANCA or c-ANCA is positive.
Rheumatoid Factor	X	
Coagulation Panel (PT, INR, APTT)	X	
Alpha-fetoprotein (AFP)	X	
AE and SAE review	X	From signing consent. AEs and SAEs that occur prior to the first administration of IMP should be recorded only if assessed as related to study participation (e.g., protocol mandated procedures or invasive tests).
Prior medication	X	

ACR = Albumin to creatinine ratio. AE = adverse event. ANCA = Anti-neutrophil cytoplasmic antibodies. APTT = Activated partial thromboplastin time. C3/C4 = Complement. COVID-19 = Coronavirus disease 2019. ECG = electrocardiogram. hs-CRP = High-sensitivity C-reactive protein. IMP = Investigational medicinal product. INR = International normalized ratio. PCR = polymerase chain reaction. PT = Prothrombin time. SAE = serious adverse event. WOCBP = Woman of childbearing potential.

CONFIDENTIAL

219239  
Protocol**Table 2** Study Session to Final Visit and Early Withdrawal

Procedure	Day										Early withdrawal	Notes
	Refer to Table 3 for acceptable time windows											
Inpatient stay	<=====>											
Outpatient visit				X	X	X	X	X	X	X		
Brief physical examination		X 	X 		X 	X	X	X	X	X		An interim symptom-targeted brief physical examination.  Within 1 h before dosing and at 24 and 72 h after dosing.
Vital signs	X	X 	X 	X 	X 	X	X	X	X	X		Blood pressure and heart rate in triplicate before dosing, and single measurements after dosing. Respiratory rate and temperature, single measurements at all time points.  Within 1 h before dosing and at 24, 48 and 72 h after dosing.
COVID-19 test	X											Using a PCR or antigen test approved by the country regulatory authorities. Test can be performed before Day –1 if required before admission for inpatient stay.
Drug, alcohol, and cotinine screen	X											As per standard local practice.
Safety 12-lead ECG	X	X 	X 	X 						X		In triplicate before dosing; single measurements after dosing.  Within 1 h before dosing and at 24 and 48 h after dosing.
Pregnancy test	X									X	X	Serum or urine. WOCBP only.
Clinical chemistry, haematology and urinalysis		X 	X 			X	X 	X 	X 	X	X	 Within 1 h before and at 24 and 72 h after dosing.  If results on Day 15 are within normal range, Day 29 and 43 tests are not required, and the next required time point is Day 64. If results on Day 15 are out of normal range, test should be repeated on Day 29; if results are still out of range on Day 29, test should be repeated on Day 43.
Urine ACR		X 	X 			X		X		X		 Within 1 h before and at 24 h after dosing.
C3, C4, hs-CRP, p-ANCA, c-ANCA		X 										 Within 1 h before dosing. Post-dose sample to be taken only if the investigator considered there was an event of vascular inflammation

CONFIDENTIAL

219239  
Protocol

Procedure	Day										Early withdrawal	Notes
CCI												
	Refer to Table 3 for acceptable time windows											
Coagulation Panel (PT, INR, APTT)		X 										 Within 1 h before dosing.
Randomization		X										
CCI dose of bepirovirsen		CCI									CCI	
CCI												
Assessment of injection site		X 	X 	X 	X 	X	X	X	X	X	X	 Within 1 h before dosing and at 24, 48 and 72 h after dosing.
CCI												
AE and SAE review	<=====>										AEs and SAEs that occur prior to the first administration of IMP should be recorded only if assessed as related to study participation (e.g., protocol mandated procedures or invasive tests).	
Prior/concomitant medication review	<=====>											

ACR = Albumin to creatinine ratio. AE = adverse event. ANCA = Anti-neutrophil cytoplasmic antibodies. APTT = Activated partial thromboplastin time. C3/C4 = Complement. COVID-19 = Coronavirus disease 2019. ECG = electrocardiogram. hs-CRP = High-sensitivity C-reactive protein. IMP = Investigational medicinal product. INR = International normalized ratio. PCR = polymerase chain reaction. PFS = prefilled syringe. PK = pharmacokinetic. PT = Prothrombin time. SAE = serious adverse event. WOCBP = Woman of childbearing potential

CONFIDENTIAL

219239  
Protocol**Table 3** Acceptable Visit/Time Point Windows

Assessment	Planned Timepoint	Acceptable window
Safety assessments*	Within 1 h before dosing	Within 90 min before dosing
	Up to Day 3	+/- 15 min
	Day 4	+/- 8 h
	Day 8 and 15	+/- 1 day
	Day 29 onwards	+/- 3 days

CCI

\*Vital signs, 12-lead ECG, clinical laboratory tests, assessment of injection site

**CONFIDENTIAL**219239  
Protocol

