## 8. **STUDY ASSESSMENTS AND PROCEDURES**

- Study procedures and their timing are summarized in the SoA (Section 1.3). Protocol waivers or exemptions are not allowed.
- Adherence to the study design requirements, including those specified in the SoA, is essential and required for study conduct.

**CONFIDENTIAL**219239  
Protocol

- All screening evaluations must be completed and reviewed to confirm that potential participants meet all eligibility criteria. Subjects who have signed informed consent but are not eligible to proceed should be recorded in the eCRF with a status of 'screen failure'.
- The maximum amount of blood collected from each participant over the duration of the study, including any extra assessments that may be required, will not exceed 500 mL.
- Repeat or unscheduled samples may be taken for safety reasons or for technical issues with the samples.

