### **8.3.5. Clinical safety laboratory tests**

- See Section [10.2](#) for the list of clinical laboratory tests to be performed in accordance with lab manual and the SoA (Section [1.3](#)).
- The investigator must review the laboratory report, document this review, and record any clinically significant changes occurring during the study as an AE. The laboratory reports must be filed with the source documents. Clinically significant

**CONFIDENTIAL**219239  
Protocol

abnormal laboratory findings are those judged at investigator discretion based on being more severe than expected for the participant's condition.

- All laboratory tests with values considered clinically significantly abnormal during participation in the study should be repeated until the values return to normal or baseline or are no longer considered clinically significantly abnormal by the investigator or Medical Monitor.
  - If such values do not return to normal/baseline within a period of time judged reasonable by the investigator, the aetiology should be identified and the Sponsor notified.
  - If laboratory values from non-protocol specified laboratory tests performed at the institution's local laboratory require a change in participant management or are considered clinically significant by the investigator (e.g., SAE or AE or dose modification), then the results must be recorded.

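### The safety laboratory row of the schedule of activities names a 72 h sample in its note but has no Day 4 mark in its grid

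*Protocol*

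**What the plan says.** Protocol Section 1.3, Table 2, has a row headed "Clinical chemistry, haematology and urinalysis". Its note 1 gives the timing around the dose as "Within 1 h before and at 24 and 72 h after dosing". The grid for that row shows a blank on Day -1, a mark with note 1 on each of Days 1 and 2, blanks on Days 3 and 4, a plain mark on Day 8, marks with note 4 on Days 15, 29 and 43, and plain marks on Day 64 and at early withdrawal.

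The brief physical examination row uses the same note number and the same three times, "Within 1 h before dosing and at 24 and 72 h after dosing". It does carry a third mark on Day 4.

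Elsewhere the protocol leaves laboratory timing to this table. Section 8.3.5 refers to the "list of clinical laboratory tests to be performed in accordance with lab manual and the SoA". Section 8 adds that "Adherence to the study design requirements, including those specified in the SoA, is essential and required for study conduct" and does not allow waivers. Table 3 sets a Day 4 window of plus or minus 8 h for a group of safety assessments that includes laboratory tests. SAP Section 6.2.3 refers back to Table 3, and SAP Section 4.5.2.2 summarises laboratory change from baseline by time point without listing the time points.

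**The concern.** The row gives two different instructions. A reader of the grid takes no scheduled chemistry, haematology or urinalysis sample between 24 h and Day 8. A reader of the note takes one at 72 h.

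The row holds ALT, platelet count and creatinine (Protocol Table 11). These bear on three of the four adverse events of special interest in Protocol Section 8.4.4: ALT increases, thrombocytopenia and renal injury. Change from baseline in laboratory tests at each time point is also the protocol's stated safety endpoint (Section 3). As written, it is undefined whether a 72 h time point belongs to that endpoint. If the ambiguity is settled informally during conduct, the 72 h summaries could be complete, empty, or filled for only some participants, and a 72 h sample could be called missing under one reading and unscheduled under the other.

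**Working it through.** No sample size or error rate is involved. The check rebuilds the redacted day headings and counts marks against named times.

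**Step 1: convert hours to study days.** Protocol Section 8.5 puts dosing at 0 h on Day 1, so day = 1 + hours/24.
- 24 h: 1 + 24/24 = Day 2
- 48 h: 1 + 48/24 = Day 3
- 72 h: 1 + 72/24 = Day 4

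**Step 2: identify the columns.** Table 2 has ten day columns, then early withdrawal and notes.
- The vital signs and injection site rows have the note "Within 1 h before dosing and at 24, 48 and 72 h after dosing" and four marks in columns 2 to 5. Those columns are therefore Days 1, 2, 3 and 4.
- The ECG row has the note "Within 1 h before dosing and at 24 and 48 h after dosing" and three marks in columns 2 to 4, which agrees.
- Laboratory note 4 starts from the Day 15 result and says "Day 29 and 43 tests are not required, and the next required time point is Day 64". Its three marks lie in columns 7 to 9 (Days 15, 29 and 43), and column 10 is Day 64.
- That leaves column 6, which is Day 8, the day between Day 4 and Day 15 in Table 3. The plain laboratory mark in column 6 is thus the Day 8 sample and cannot stand for 72 h.

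**Step 3: compare times named with marks shown.**

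| Row | Times named in note | Marks with that note | Days marked |
|---|---|---|---|
| Brief physical examination | 3 | 3 | 1, 2, 4 |
| Vital signs | 4 | 4 | 1, 2, 3, 4 |
| ECG | 3 | 3 | 1, 2, 3 |
| Urine ACR | 2 | 2 | 1, 2 |
| Injection site | 4 | 4 | 1, 2, 3, 4 |
| **Chemistry, haematology, urinalysis** | **3** | **2** | **1, 2** |

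Only the laboratory row falls short, by 3 - 2 = 1 mark. The shortfall does not depend on the column mapping, because two marks cannot cover three named times.

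**Step 4: gap between scheduled safety laboratory samples.**
- Grid: 8 - 2 = 6 days.
- Note: 4 - 2 = 2 days, then 8 - 4 = 4 days.

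**Step 5: look for text that settles it.** Sections 8.3 and 8.3.5 defer to the schedule. The Day 4 window in Table 3 does not schedule a sample: the group it covers also includes ECG, which has no Day 4 mark. Urine ACR has its own note limited to pre-dose and 24 h, so the authors did distinguish a two-time pattern from a three-time pattern, but this does not show which one the laboratory row was meant to have.

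**The case against.** The strongest objection is that the table was read from a PDF and its day headings are redacted, so a single mark could have been lost. The same grid has one oddity: the outpatient row is marked in the column identified as Day 3, although Section 4.1 keeps participants as inpatients until Day 3. That may be a discharge-day convention, an error in the protocol or an extraction fault. Against a shifted row, the laboratory row has its full set of cells and its later marks fall where note 4 puts them. A single lost mark cannot be excluded, so the original page must be checked.

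Other points limit the consequence:
- The two readings are not equally serious. Sections 8, 8.3 and 10.2 allow unscheduled or additional safety tests, so an extra 72 h sample is less clearly a deviation than an omitted one. None of these provisions orders a routine 72 h sample for everyone.
- The laboratory manual, which Section 8.3.5 also cites, is not available here and may give collection times. That could keep conduct uniform, but it would not remove the conflict inside the protocol.
- The number of sites is not given, so divergence between sites is a possibility and has not been shown.
- Samples at pre-dose, 24 h, Day 8, Day 15 and Day 64 stand under either reading. Event-driven checks also remain, such as a prompt platelet count if signs of thrombocytopenia appear (Section 7.1.2).

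These points bear on certainty and scale. None of them reconciles the note with the grid.

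**Conclusion.** The concern holds. On the text available, the laboratory note requires a 72 h sample that the grid does not schedule, and nothing else in the protocol or SAP decides between them. It affects every participant: one of the two early post-dose safety samples named in the note, with a scheduled gap of either 6 days or 2 and then 4 days.

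The consequence is confined to early safety laboratory data and their by-time-point summaries, which are descriptive. The primary and secondary endpoints, Cmax and AUC(0-inf), are not affected. The correction should be made, but it does not threaten the trial's main conclusions.

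The conclusion rests on two assumptions: that no mark was lost in extraction, and that the redacted headings are Days -1, 1, 2, 3, 4, 8, 15, 29, 43 and 64, as the notes imply. The documents do not show whether the note or the grid is the intended schedule.

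**What to change.** Check the laboratory row on the original page. If the Day 4 mark is absent there too, the sponsor should decide which schedule is intended and correct either the grid cell or note 1 so that both state the same post-dose times. The agreed times should then be carried into the eCRF visit schedule, the laboratory manual and an explicit list of laboratory time points in the SAP or its output specification.

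The cost is one table cell or one clause of a note, with the matching updates. Table 2 already has an outpatient visit and a brief physical examination on Day 4, so neither resolution needs a new visit.

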**Table 4 Risk Assessment**

Potential Risk of Clinical Significance	Summary of Data/Rationale for Risk	Mitigation Strategy
Study Intervention(s) [Bepirovirsen]		
Non-clinical Risks:		
Drug Induced Vascular Inflammation (DIVI) and Complement Activation	Inflammatory and immune changes are recognized as a class effect of ASOs. Vasculitis and/or perivascular inflammation has been described in monkey studies with many, if not most ASOs. DIVI has not been observed in clinical studies with bepirovirsen to date.	Laboratory Evaluations: Inclusion of tests for biomarkers of inflammation/complement activation that would be expected to accompany vascular injury are to be taken at the time of a clinical event that is suggestive of vasculitis and/or immune activation and compared to referenced baseline measurements. A monitoring strategy is included (see Section 7.1.4 ).
Clinical Risks:		
Serious liver injury	The liver is a site of accumulation of ASOs. Liver findings in nonclinical studies of bepirovirsen were generally limited to mild hepatic enzyme elevations associated with hepatic vacuolation without concomitant histologic evidence of degeneration in mice, consistent with findings noted with other 2'-methoxyethyl (MOE) ASOs. Review of the	The risk of serious liver injury is very low after a single dose of bepirovirsen. Nevertheless, hepatic enzyme monitoring will be performed (see Section 7.1.1 ).

CONFIDENTIAL

219239  
Protocol

Potential Risk of Clinical Significance	Summary of Data/Rationale for Risk	Mitigation Strategy
	
available clinical data indicates liver enzymes are increased on treatment with ASOs (for treatment of diseases other than chronic HBV infection) in a low percentage of patients compared to placebo. A prior single dose study in healthy volunteers (213725) did result in an ALT increase > ULN in 1 participant treated with CC1 mg bepirovirsen. This was not associated with other changes in liver chemistry (e.g., bilirubin, INR) and did not have a clinical consequence. Review of AE data and laboratory data in Phase 2a and Phase 2b studies in participants with CHB in which bepirovirsen was given weekly for 4 weeks and 24 weeks respectively and where ALT increases > 3xULN were observed, showed no evidence of DILI.
 
CC1
	

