### 7.1.3. Drug induced kidney injury (renal) monitoring

If any of the following are observed, results should be confirmed (with a new blood sample), and if confirmed, further evaluation for alternative causes should be pursued in consultation with the Medical Monitor:

- Persistent uACR  $> 0.3 \text{ mg/mg}$  ( $> 300 \text{ mg/g}$ )
- Blood in urinalysis  $> 5$  red blood cells per high power field confirmed by urine microscopy (unless there is a known cause [e.g., females during menstruation])
- Gradual and consistent reductions of eGFR compared with baseline.

Following confirmation of the criteria above, if underlying cause other than drug-induced renal injury is not confirmed, further evaluation may include but not be limited to a 24 hour urine analysis, consultation with a nephrology specialist, renal ultrasound, urine microscopy, serum urea and creatinine, platelet count, urgent serum vasculitis screen (including ANCA, ANA, dsDNA, Rheumatoid Factor, cryoglobulins), SPEP/UPEP, and complement panel (C3, C4, C5a and Bb). Further evaluation and actions should be determined by the investigator in consultation with the Medical Monitor.

**CONFIDENTIAL**219239  
Protocol

Participants must be monitored weekly until uACR or eGFR resolve, stabilize, or return to within baseline values.

If acute glomerulonephritis is confirmed or probable [i.e., meets clinical definition of RPGN if biopsy not feasible], delay in treatment of suspected RPGN should be avoided.

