#### **7.1.4. Drug induced vascular injury and complement activation**

If the participant develops signs/symptoms of potential complement activation/DIVI including (but not limited to) new onset: persistent joint pain not resolved with simple analgesia, peripheral neuropathy, vasculitis/purpuric rash, signs of renal involvement, for example (haematuria; increasing presence of blood on urine microscopy, increasing urine ACR, rising creatinine, falling GFR), jaundice, haemolysis and/or thrombocytopenia, in addition to relevant investigations based on the participant's symptoms and signs, the following tests should also be conducted: C3, C4, Factor Bb, C5a, Rheumatoid factor, cryoglobulins (locally if available), ANCA, SPEP, UPEP, hs-CRP and compared to baseline values, if available.

Additional complement analyses for example CH50, Factor Bb level, Factor H level, sC5b-9 and samples for MCP-1 should also be considered in discussion with the Medical Monitor (who may consult with the internal Safety Panels).

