##### **8.4.4.2. Vascular Inflammation and complement activation**

Inflammatory and immune changes are recognized as a class effect of ASOs. Despite the low risk for ASO-related vascular AEs in participants, the nature of the toxicity demands a conservative approach to care and monitoring to ensure the safety of participants.

**CONFIDENTIAL**219239  
Protocol

A monitoring strategy is presented in [7.1.4](#)

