4.5.2.3. Monitoring Event Reporting

Liver monitoring and stopping event reporting will be summarized and listed. The Liver monitoring and stopping criteria are described in the protocol Section 7.1.1.

Haematological monitoring will be summarized and listed based on laboratory parameters (platelet count and anti-platelet antibodies). The haematological monitoring criteria are described in the protocol Section 7.1.2.

Data for potential Drug induced kidney injury (renal) monitoring events will be captured in the eCRF; they will be summarized. The kidney injury monitoring criteria are described in the protocol Section 7.1.3.

Data for potential drug induced vascular injury and complement monitoring will be captured in the eCRF; they will be summarized. The drug induced vascular injury and complement monitoring criteria are described in the protocol Section 7.1.4.

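### The schedule's note on post-dose C3, C4, hs-CRP and ANCA sets a narrower trigger than Section 7.1.4 and should be brought into line with it

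*Protocol*

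**What the plan says.** Protocol Section 1.3, Table 2, schedules C3, C4, hs-CRP, p-ANCA and c-ANCA once, before dosing on Day 1. Note 6 on that row then adds: "Post-dose sample to be taken only if the investigator considered there was an event of vascular inflammation". It does not refer to any other section.

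Protocol Section 7.1.4 sets the monitoring rule for vascular injury and complement activation. Its trigger is: "If the participant develops signs/symptoms of potential complement activation/DIVI including (but not limited to) new onset", followed by a list of presentations. Its action is: "the following tests should also be conducted: C3, C4, Factor Bb, C5a, Rheumatoid factor, cryoglobulins (locally if available), ANCA, SPEP, UPEP, hs-CRP", with the results compared with baseline where a baseline exists.

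Three other places bear on which rule is intended:

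- Table 4 (Section 2.3.1) says the biomarkers are to be taken "at the time of a clinical event that is suggestive of vasculitis and/or immune activation and compared to referenced baseline measurements", and refers to 7.1.4.
- Section 8.4.4.2, on this adverse event of special interest, says "the nature of the toxicity demands a conservative approach to care and monitoring to ensure the safety of participants", and refers to 7.1.4.
- SAP Section 4.5.2.3 states: "The drug induced vascular injury and complement monitoring criteria are described in the protocol Section 7.1.4".

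Section 8 of the protocol says of the schedule: "Adherence to the study design requirements, including those specified in the SoA, is essential and required for study conduct".

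**The concern.** Two complete, unredacted sentences give different triggers for the same blood tests. The note requires the investigator to have concluded that vascular inflammation occurred. Section 7.1.4 requires only signs or symptoms that could point to complement activation or vascular inflammation.

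The order in the note is also awkward. Table 4 describes these markers as ones expected to accompany vascular injury, so the result ought to inform the investigator's judgement and not wait for it.

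A site working from the schedule and following the note literally could leave out the post-dose sample in a participant with early or atypical signs. If the event is transient, the sample cannot be recovered later, and the comparison with the pre-dose value is lost with it. At stake are the safety work-up of a healthy volunteer, who gains no direct benefit from the trial, and the characterisation of an adverse event of special interest.

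**Working it through.** There is no plan figure to reproduce. The check sets the two rules side by side and counts from the text.

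**The two rules**

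| | Table 2, note 6 | Section 7.1.4 |
|---|---|---|
| Threshold | Investigator considered that an event had occurred | Signs or symptoms of a potential event |
| Scope | Vascular inflammation | Complement activation and DIVI |
| Force | Sample only in that case | Tests should be done |
| Cross-reference | None | Cited by Table 4, Section 8.4.4.2 and SAP 4.5.2.3 |

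**Presentations named in 7.1.4.** These are joint pain, peripheral neuropathy, vasculitis/purpuric rash, renal signs, jaundice, haemolysis and thrombocytopenia, 7 in all. One of them (vasculitis/purpuric rash) is vascular inflammation in itself. The remainder is 7 − 1 = 6, for which 7.1.4 asks for the tests while the note does not necessarily allow them. Isolated haemolysis or thrombocytopenia is the clearest case.

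**Tests named in 7.1.4.** These are C3, C4, Factor Bb, C5a, rheumatoid factor, cryoglobulins, ANCA, SPEP, UPEP and hs-CRP, 10 in all. Against the readable rows of Tables 1 and 2:

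- In the note 6 row, with a Day 1 pre-dose value: C3, C4, hs-CRP, ANCA = 4.
- Screening value only: rheumatoid factor = 1.
- No scheduled baseline visible: Factor Bb, C5a, cryoglobulins, SPEP, UPEP = 5.
- Total: 4 + 1 + 5 = 10.

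So the four tests that the note restricts are, as far as can be seen, the ones for which a before-and-after comparison is best supported.

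**Do other sections supply the tests anyway?**

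- *Platelets (Section 7.1.2, Table 7):* repeat counts and anti-platelet antibodies. None of the four is named.
- *Liver (Section 7.1.1, Appendix 6), relevant to jaundice:* none of the four is named.
- *Renal (Section 7.1.3):* ANCA and C3/C4 are listed, but only after the renal criteria are confirmed and only as an option ("further evaluation may include but not be limited to a 24 hour urine analysis"). hs-CRP is not listed.
- *General allowances (Sections 8 and 8.3, Appendix 2):* unscheduled or additional safety tests are permitted. None of these clauses calls for this panel or removes the restriction in the note.

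**The case against.** The strongest reply is that Section 7.1.4 already governs. It is a dedicated monitoring section, three other places refer to it, and a site that omitted the panel would be departing from it. Section 8 describes the schedule as a summary of procedures, and its adherence clause does not place the schedule above the body text. On this view the note only tells sites that there is no routine post-dose draw. A site acting on a suspected event would also have to open 7.1.4 to learn about Factor Bb, C5a and the rest, and would find C3, C4, ANCA and hs-CRP in the same sentence.

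Much of this stands. It shows that the intended rule is clear and that a missed sample is a possibility, not a likelihood. It does not remove the conflict. The protocol has no rule saying which text prevails, and a reader of the schedule row meets a restriction with no pointer elsewhere. A lenient reader may take the word considered to include suspicion, but that does not restore complement activation, which the note omits.

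Two cautions about the counts are fair. The list in 7.1.4 is open-ended, and an investigator might judge renal signs, neuropathy or joint pain to be vascular inflammation, so 6 of 7 describes the named examples and is not a rate of missed tests. Table 2 also has redacted rows, so the statement that five tests have no baseline holds only for the rows that can be read.

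**Conclusion.** The concern holds: note 6 is wrong as written. It sets a higher threshold and a narrower scope than Section 7.1.4, and it is the only one of these texts that does so. In terms of the named examples, 6 of 7 presentations and 4 of 10 tests are affected.

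The practical consequence is limited. Section 2.3.1 describes the risks at this dose as unlikely, and Table 4 reports no DIVI in bepirovirsen clinical studies so far. The PK analyses do not depend on this panel. Under SAP Section 4.5.1.1, adverse events of special interest are identified from MedDRA terms, so a missing panel does not in itself remove an event from the counts. The loss would fall on the individual work-up and on the description of the event.

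The conclusion assumes that some site staff will follow the note literally; the documents do not show how often that would happen. The point should be corrected, but it does not threaten the primary objective.

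**What to change.** In Table 2, on the C3, C4, hs-CRP, p-ANCA and c-ANCA row, replace the second sentence of note 6 with:

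> Draw a post-dose sample if signs or symptoms of possible complement activation or DIVI develop; see Section 7.1.4.

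The edit should name the row, because the coagulation row also carries a note 6; that one has only the pre-dose timing and needs no change. Dropping the word only leaves the renal route in Section 7.1.3 open, and a reference to 7.1.3 could be added.

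The cost is one footnote sentence. Samples are still drawn only when a sign or symptom occurs, so routine burden is unchanged, and the SAP needs no amendment because it already relies on Section 7.1.4.
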